9.4 Withdrawal of individual subjects

Subjects can immediately withdraw from participating to the study at any time for any reason without any consequences. The investigator can decide to withdraw a subject from the study for urgent medical reasons.

9.4.1 Specific criteria for withdrawal

We do not expect specific complaints or side effects of the VR treatment which are reasons to withdraw from the study. Whenever dangerous situations would occur, for example an epileptic insult, the patient will be withdrawn from the study.

9.5 Replacement of individual subjects after withdrawal

After withdrawal of a participant, it is not possible to replace this patient with a new participant.

9.6 Follow-up of subjects withdrawn from treatment

After withdrawal from a participant in case of the VR-group or standard care-group, then the patient is asked to agree with obtaining the measurements (NRS score, anxiety score etc) and using this data. When she wants to withdraw completely, then she can be replaced by a new patient.

When a patient only wants to withdraw from treatment, thus VR intervention, and agrees with the measurements, then the data will be included in the analyses.

9.7 Premature termination of the study

We do not expect the study has to be terminated premature before enrolling the required participants. No interim analysis will be performed because of the small number of subjects that have to be included.

10. SAFETY REPORTING

10.1 Temporary halt for reasons of subject safety

In accordance to section 10, subsection 4, of the WMO, the sponsor will suspend the study if there is sufficient ground that continuation of the study will jeopardize subject health or safety. The sponsor will notify the accredited METC without undue delay of a temporary halt including the reason for such an action. The study will be suspended pending a further positive decision by the accredited METC. The investigator will take care that all subjects are kept informed.

10.2 AEs, SAEs and SUSARs

10.2.1 Adverse events (AEs)

Adverse events are defined as any undesirable experience occurring to a subject during the study, whether or not considered related to intervention. All adverse events reported spontaneously by the subject or observed by the investigator or his staff will be recorded. Given the negligible risk on side effects we decided not standard register adverse events (AE).

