The State-Trait Anxiety Inventory-6 questionnaire is a short questionnaire about the feelings of a person in that specific moment [17]. It consists of questions about anxiety, satisfaction and worries. Women were asked to rank on a 4-point scale (0= not at all, 4 = completely) reflecting on the feelings in that specific moment. To calculate the total STAI score, you have to reverse scoring of positive items (calm, relax, content etc) so 1=4 points, 2=3 points, 3=2 points, 4=1points. You can sum all the scores, multiply the total score by 20 and divide this by 6 [17]. The score ranges from 20 to 90 and the higher the score the more anxiety the person experiences. The STAI questionnaire shows the experience of anxiety at baseline.

Pain catastrophizing (Pain Catastrophizing Scale questionnaire) (see attachment 4)

The pain catastrophizing scale (PCS) has been designed to assess three various dimensions of catastrophizing concerning rumination, magnification and helplessness. It consists of 13 statements describing different feelings and thoughts that can be experienced when in pain. Women were asked to rank on a five-point scale (0 = not at all; 4 = all the time) reflecting on a painful experience in the past [18]. The subscales of the PCS can be calculated separately or overall with a maximum total score of 52 [18, 19]. The higher the score, the more catastrophizing thoughts are present. (see attachments for full questionnaire). The PCS shows how people are able to cope with pain and various thoughts.

NRS:

How did you experience the pain after the surgery?

Anxiety:

How frightened were you after surgery?

VR- questionnaire (see attachment 5)

After the surgery, at the medical ward, a questionnaire will be given to evaluate the experience of VR.

Study schedule

	Informed consent	Baseline questionnaire	PCS and STAI	Pain score (NRS)	Anxiety score (NRS)
Outpatient clinic					
Preoperative (T0) 1. VR-group 2. Standard care group					
Preoperative (T1) 1. VR: before VR intervention (T1A) 2. VR: after VR intervention (T1B) 3. Standard care-group (T1A) 4. Standard care-group after 10-15min (T1B)					
Postoperative (T2), after arriving on recovery 1. VR-group 2. Standard care-group					
Postoperative (T3) before leaving recovery 1. VR- group 2. Standard care- group					

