10.4 Follow-up of adverse events

All AEs will be followed until they have abated, or until a stable situation has been reached. Depending on the event, follow up may require additional tests or medical procedures as indicated, and/or referral to the general physician or a medical specialist.

SAEs need to be reported till end of study within the Netherlands, as defined in the protocol.

10.5 [Data Safety Monitoring Board (DSMB) / Safety Committee]

No DSMB will be necessary.

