11.2 Secondary study parameter(s)

The differences in NRS-scores pre- and postoperative of anxiety in both groups (VR-intervention and standard-care group) will be analyzed using the linear mixed models analysis. The results of the STAI-questionnaire, PCS questionnaire, analgesic use and length of hospital stay will be calculated into means with standard deviation and confidence interval. We want to compare the baseline characteristics and questionnaires (STAI and PCS) to see whether the groups are equally divided. The STAI and PCS questionnaire are continuous variables, we will use the independent sample t-test. The tolerability, feasibility and satisfaction of VR use will be calculated into means and frequencies.

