12.4 Benefits and risks assessment, group relatedness

The risks of this research will be small, according to the CTCM. Possible rare side-effects of the use of VR can be: nausea, dizziness and vomiting. Whenever a patient experiences side-effects or hindrance of the study, she can decide to withdraw. Benefits of the study: probably less pain after gynecological surgery with spinal anesthesia and less anxiety in the pre- and postoperative setting.

Previous studies reported transient adverse events such as nausea and dizziness, but no major adverse events [20-24]. The risks of VR therapy for the participants are negligible. Previous studies described significant reductions of acute pain scores after a single VR session.

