Attachment 5. VR-questionnaire

We would like to ask you some questions about your experience with Virtual Reality (VR).

1. How did you experience the use of VR before surgery?

- Very pleasant
- Pleasant
- Neutral
- Unpleasant
- Very unpleasant

2. How did you experience the use of VR after your surgery?

- Very pleasant
- Pleasant
- Neutral
- Unpleasant
- Very unpleasant

3. Did the VR-experience contribute in reducing your pain experience before your surgery?

- Very likely
- Likely
- Pretty likely
- Not likely
- Not likely at all

4. Did the VR-experience contribute in reducing your pain experience after your surgery?

- Very likely
- Likely
- Pretty likely
- Not likely
- Not likely at all

5. Did the VR-experience reduce your anxiety level before surgery?

- Very likely
- Likely
- Pretty likely
- Not likely
- Not likely at all

6. Did the VR-experience reduce your anxiety level after the surgery?

- Very likely
- Likely
- Pretty likely
- Not likely
- Not likely at all

7. Would you choose the use of VR during a surgery under spinal anesthesia the next time you will have to get surgery?

- Very likely
- Likely
- Pretty likely
- Not likely
- Not likely at all

8. The use of the VR-app is easy:

- Completely agree

- Agree
- Neutral
- Disagree
- Completely disagree

9. Would you recommend the use of VR during a surgery under spinal anesthesia to your friends, family or others?

- Very likely
- Likely
- Pretty likely
- Not likely
- Not likely at all

10. How easy was the use of VR before or after surgery?

- Very easy
- Easy
- Pretty easy
- Not that easy
- Not easy at all

11. How visually attractive was the VR-experience before and after surgery

- Very attractive
- Attractive
- Pretty attractive
- Not that attractive
- Not attractive at all

12. Did you prefer anything else in the VR-app?

- No
- Yes, if yes circle what you prefer,

A more active game component
A less active game component
Only relaxing images

13. Did you experience any side-effects during the use of the VR-app?

- No
- Yes, if yes circle the side-effects;

Nausea
Dizziness
Other:

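### The adverse-event recording rule in 10.2.1 and 10.4 needs reconciling, and prompting side effects only in VR users limits what the tolerability outcome can show.

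*Combined protocol and SAP*

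**What the plan says.** **Recording.** Section 10.2.1 defines an AE as any undesirable experience of a subject during the study, related or not, with no restriction by arm. It continues: "All adverse events reported spontaneously by the subject or observed by the investigator or his staff will be recorded". The next sentence reads: "Given the negligible risk on side effects we decided not standard register adverse events (AE". Section 10.4 adds: "All AEs will be followed until they have abated, or until a stable situation has been reached". Serious adverse events have their own reporting rule in 10.2.2.

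**Tolerability.** Sections 3 and 9.1.2 list tolerability, feasibility and satisfaction of VR use, measured by questionnaire, as a secondary outcome. Section 9.3 gives the timing: "After the surgery, at the medical ward, a questionnaire will be given to evaluate the experience of VR". Item 13 of that form (Attachment 5) asks "Did you experience any side-effects during the use of the VR-app" and offers nausea, dizziness and other. Items 1 to 6 ask about the periods before and after surgery separately; item 1, for example, is "How did you experience the use of VR before surgery". Item 13 makes no such split. Section 11.2 plans a summary only: "The tolerability, feasibility and satisfaction of VR use will be calculated into means and frequencies".

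**Background symptoms.** Section 12.4 states: "Possible rare side-effects of the use of VR can be: nausea, dizziness and vomiting". The standard pain protocol (6.1 and 9.3), which both arms receive, gives nausea as an example of why a postoperative oral drug may not be possible. No rate is given anywhere.

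**The concern.** There are two separate issues.

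First, a staff member who sees a dizzy or nauseated patient cannot tell from 10.2.1 alone whether to make an entry, because two adjacent sentences point in different directions. Section 10.4 then requires follow-up of events that may never have been written down.

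Second, the trial has a randomised control group but does not use it for the symptoms that the protocol itself names as VR side effects. VR users are asked a direct question. For standard-care patients the documents describe at most unprompted capture. A reader of the final report will see a nausea frequency in VR users and cannot judge how much would have occurred without VR, or whether it arose in the preoperative session or after surgery and analgesics.

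**Working it through.** The plan states no AE rate, so there is no figure to reproduce. The check is a comparison of texts followed by illustrative arithmetic.

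**1. The recording rule.**
- 10.2.1, recording sentence: spontaneous or observed AEs are recorded.
- 10.2.1, following sentence: AEs are not registered as standard.
- 10.4: all AEs are followed.

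The direct conflict is between the two sentences of 10.2.1. Section 10.4 conflicts only by implication. All three fit together if AEs are captured passively, are not systematically sought, and 10.4 applies to those recorded. No sentence says so.

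**2. Who is asked, and when.** The T0 to T3 schedule in 9.3 holds the baseline form, STAI-6, PCS, and pain and anxiety scores. It has no symptom item for either arm. The only prompted item is item 13. The text does not expressly confine the form to the VR arm, but its title, purpose and wording do. As planned, up to 30 VR patients and no control patients are asked. One answer covers a preoperative session and one or two recovery-ward sessions (6.1).

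**3. What unequal capture could do (assumed values).** Suppose the true nausea rate p is equal in both arms, prompting captures every case, and spontaneous reporting captures a share s between 0 and 0.5. Expected counts are 30p for VR and 30ps for standard care. The spurious difference is p(1 − s).

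| p | VR | Standard care | Spurious difference |
|---|---|---|---|
| 10% | 3.0/30 | 0 to 1.5/30 | 5 to 10 points |
| 20% | 6.0/30 | 0 to 3.0/30 | 10 to 20 points |
| 30% | 9.0/30 | 0 to 4.5/30 | 15 to 30 points |

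The plan does not make this comparison. The table shows why a reader could not make it either. With equal prompting and equal reporting, the expected difference is 0.

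**4. Precision if both arms were asked.** Inputs: 30 per arm, or 26 if the whole loss allowance in 5.4 is used up; equal rates p are assumed. The Wald 95% half-width is 1.96·√(2p(1 − p)/n).
- n = 30, p = 10%: 1.96·√(0.18/30) = 0.152
- n = 30, p = 20%: 1.96·√(0.32/30) = 0.202
- n = 30, p = 30%: 1.96·√(0.42/30) = 0.232
- n = 26, same rates: 0.163, 0.217 and 0.249

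Newcombe half-widths at 3/30, 6/30 and 9/30 in both arms are 0.169, 0.202 and 0.223, much the same. For sparse data, Newcombe intervals for the risk difference are −3 to 26 points for 3/30 against 0/30, and −11 to 11 points for 0/30 against 0/30.

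**The case against.** The best defence is that the plan is coherent on its own terms. Passive capture is a natural reading of 10.2.1, the AE definition covers every subject, and 10.4 then applies to whatever is recorded. Tolerability is declared as a property of VR use, measured by a questionnaire and summarised descriptively. No between-arm comparison is planned, and item 13 asks about effects during use of the app, not about perioperative nausea in general. The evidence for background nausea is one parenthetical example, postoperative only, without a rate and without dizziness. Data from 30 per arm would be imprecise, and in an open-label trial identical questions need not draw comparable answers.

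Most of this stands, and it limits the point. A reader might infer that AEs go unrecorded, that control-arm events are excluded, or that SAE reporting is weakened. The text supports none of these: 10.2.1 has no arm restriction and 10.2.2 is separate. A reader might also infer a breach of the analysis plan or harm to the pain comparison. Neither follows, since 11.2 promises only description and the primary outcome does not use these data. Nor do the documents show that nausea is common in both arms; they only foresee it after surgery.

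Two things survive. The passive-capture reading has to be supplied by the reader. And the item 13 window does not establish cause: a patient nauseated on the recovery ward for another reason can truthfully report nausea during VR.

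**Conclusion.** The point holds as a request for clarification plus a modest limitation of design. Sections 10.2.1 and 10.4 should be reconciled into one rule. The item 13 frequency will describe what VR users report, but it cannot show how much occurs without VR, nor separate preoperative from postoperative sessions. The consequence is confined to the interpretation of one descriptive secondary outcome.

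The size of any distortion is unknown, because it depends on a nausea rate and a spontaneous-reporting share that the documents do not give. Under the assumptions above, a naive contrast could be off by 5 to 30 points. It would be wrong to infer that asking both arms turns this into a safety test. With half-widths of about 15 to 23 points at 30 per arm, a result near zero would not rule out a material excess.

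**What to change.** **Main change (one or two sentences).** State in 10.2.1 a single recording rule that applies to both arms, and say in 10.4 that follow-up covers recorded AEs. If passive capture is meant, say that spontaneously reported or observed AEs are recorded in both arms and that AEs are not otherwise actively sought, apart from any listed items.

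**Cheap improvement.**
- Put the same yes/no items on nausea, dizziness and vomiting to both arms at T1a, T1b, T2 and T3, where pain and anxiety are already scored.
- Fix the look-back: present now at T1a and T2; new since the previous score at T1b and T3. T1a and T2 then serve as baselines for T1b and T3.
- Report counts by arm with the risk difference and 95% Newcombe interval, labelled descriptive.
- Keep item 13 as VR-only information, split into before and after surgery like items 1 to 6.

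**Cost and limits.** Three tick-boxes at four existing contacts and slightly more data entry. Prompting may raise reported rates, and open-label reporting may still differ by arm. T3 needs cautious reading because of analgesics, variable stay and a possible second VR session. The documents do not say whether spinal anesthesia is given before T1b, so that timing should be noted in both arms. The report should state that low precision does not allow a conclusion of no excess.

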10.2.2 Serious adverse events (SAEs)

A serious adverse event is any untoward medical occurrence or effect that

- results in death;
- is life threatening (at the time of the event);
- requires hospitalisation or prolongation of existing inpatients' hospitalisation;
- results in persistent or significant disability or incapacity;
- any other important medical event that did not result in any of the outcomes listed above due to medical or surgical intervention but could have been based upon appropriate judgement by the investigator.

An elective hospital admission will not be considered as a serious adverse event.

May a serious adverse event occur, this will be reported by the head-investigator within one week after the event at the website <http://www.toetsingonline.nl>.

10.2.3 Suspected unexpected serious adverse reactions (SUSARs)

Not applicable

10.3 Annual safety report

Not applicable.

10.4 Follow-up of adverse events

All AEs will be followed until they have abated, or until a stable situation has been reached. Depending on the event, follow up may require additional tests or medical procedures as indicated, and/or referral to the general physician or a medical specialist.

SAEs need to be reported till end of study within the Netherlands, as defined in the protocol.

10.5 [Data Safety Monitoring Board (DSMB) / Safety Committee]

No DSMB will be necessary.

11. STATISTICAL ANALYSIS

The data will be analyzed using the program SPSS (version 22). A Chi-square test will be used to assess categorical variables, and the independent sample T-test will be used for continuous variables in case of normal distribution based on the skewness, kurtosis, and graphical representation (histogram) of the continuous variables. The mean NRS-score with standard deviation will be calculated for pain as well as anxiety in both groups, when the data is normally divided. When the data is not normally divided, then a median with interquartile range will be calculated. For categorical variables, frequency and percentage will be calculated. Depending on the amount of missing values, the missing values will be excluded or imputed. This depends on the amount of missing values.

11.1 Primary study parameter(s)

The differences in postoperative NRS-scores of pain in between both groups (VR-intervention and standard-care group) will be analyzed using the linear mixed models analysis. The NRS-score of pain of the VR group and standard-care group will be compared to see whether VR influences the pain experience. Different variables, like age, BMI, ethnicity, education level, marital status, vaginal parity, ASA-classification, medication use, intoxications, chronic pain, surgical history, indication of surgery, type of planned surgery, will be considered in the statistical analysis. These are taken into account because these variables can be possible confounders in the results of the study.

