3. OBJECTIVES

The aim of this study is to determine whether VR used in the immediate postoperative period after gynecological surgery will decrease pain scores.

Primary Outcome measure: reduction in postoperative pain score (NRS, numeric rating scale)

Secondary Outcome measures:

- Pre-operative anxiety (State-Trait Anxiety Inventory (STAI)-6 questionnaire)
- Pain catastrophizing (Pain Catastrophizing Scale questionnaire)
- Difference in anxiety scores pre-and post VR intervention (NRS)
- Analgesic use (daily use of paracetamol, NSAIDs, opioids)
- Length of hospital stay
- Tolerability, feasibility and satisfaction of VR use (questionnaire)
- Preoperative pain score (NRS)

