5.3 Exclusion criteria

- Chronic pain patients; defined as 'persistent or recurrent pain lasting longer than 3 months' [16]. The pain is not due to the gynecological problem.
- Chronical use of pain medication (opioids)
- History of prior opioid use defined as use within 8 to 90 days prior to the surgical procedure
- Alcohol or drug abuse
- Known car sickness
- Epileptic insults in previous history
- Psychotically seizures in previous history
- Claustrophobic
- Blindness
- History of mental illness

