9.1.2 Secondary study parameters

Secondary outcomes will be:

- Pre-operative anxiety (State-Trait Anxiety Inventory (STAI)-6 questionnaire)
- Pain catastrophizing (Pain Catastrophizing Scale questionnaire)
- Difference in anxiety scores pre- and post VR intervention (NRS)
- Analgesic use (daily use of paracetamol, NSAIDs, opioids)
- Length of hospital stay
- Tolerability, feasibility and satisfaction of VR use (questionnaire)
- Preoperative pain score (NRS)

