9.3 Study procedures

Patients who were planned for elective gynecological surgery under spinal anesthesia will be informed about the study during their visit at the outpatient clinic. Eligible patients who fulfill the inclusion criteria will be identified and counselled by the research coordinator or staff of the Zuyderland Medical Centre.

Before entry into the study, the research coordinator and/or the staff will explain to potential participants the aims, methods, reasonably anticipated benefits, and potential hazards of the study. They will be informed that their participation is voluntary and that they may withdraw consent to participate at any time during the study. They will be informed that choosing not to participate will not affect their care. After giving sufficient information, written informed consent must be obtained.

After receiving written informed consent and before randomisation, pre-operatively a baseline questionnaire pre-operative anxiety (STAI-6 questionnaire) and pain catastrophizing scale (PCS) questionnaire (T0) will be filled in pre-operatively on the ward. Subsequently the randomisation procedure will be proceeded.

Intervention (VR-group)

The participant can choose a VR- intervention of own preference. They can choose between an immersive guided relaxation or an interactive VR experience. A total of four scenarios can be chosen;

1. Interactive mini-games, such as a game in which the patient immerses into a 360 environment (e.g. Erasmus Bridge Rotterdam), and is asked to guess the name of this environment
2. Mindfulness exercises, in which the patient immerses into relaxing environments and is guided by a mindfulness coach (i.e. guided audio);
3. 360-videos of either relaxing or stimulating environments
4. Speedreading exercises, in which the participant is challenged to read certain articles at his/her highest possible reading speed (in words per minute).

The VR-glasses will be used following the VR-hygiene protocol (see attachment 1).

The participants in the intervention group will also receive the usual standard pre- and postoperative management including the standard pain protocol.

Standard care- group:

The participants randomised into the standard care- group will receive the usual standard pre-and postoperative management.

Standard pain protocol:

1. Preoperative (arrival day-care unit) start with 1000mg paracetamol orally administered.

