Attachment 2. Baseline characteristics

Age, BMI, ethnicity, education level, marital status, vaginal parity, ASA-classification, medication use, intoxications, chronic pain, surgical history, indication of surgery

1. Age

..... years

2. Length

..... cm

3. Weight

.....kg

4. Etnicity (when you rather not fulfill this question, you can fil in 'unknown')

- Kaukasian
- Latin-American
- Azian
- African
- Turkish
- Other ethnicity
- Unknown

5. Education (when you rather not fulfill this question, you can fil in 'unknown')

- Primary school
- High school
- Community college
- University
- Unknown

6. Marital status (when you rather not fulfill this question, you can fil in 'unknown')

- Single
- Living together
- Married
- Unknown

7. Smoking

- Yes,..... sigars/sigarrettes per day/week/month
- No

8. Alcohol

- Yes,..... glasses per day/week/month
- No

9. Drugs

- Yes,..... per day/week/month
- No

10. Vaginal delivery's

- 0
- 1
- 2
- 3
- 4
- >5

11. Medication use

.....

12. When using medication, do you use morphine? (e.g. oxycodon, oxycontin, morphine, fentanyl or others?)

.....

13. Do you have chronic pain (existing for more than 6 months) not related to the reason of the surgery?

- Yes
- No

14. Have you ever had surgery before?

- Yes
- No

15. When you answered 'yes' on question 14, what kind of surgery did you have?

.....

16. ASA classification (will be filled in by your doctor)

- ASA 1
- ASA 2
- ASA 3
- ASA 4

17. Indication of surgery (will be filled in by your doctor)

.....

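### The primary pain model rests on an open list of 13 possible confounders instead of a fixed covariate set, and two questionnaires taken only before randomisation are listed as outcomes

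*Combined protocol and SAP*

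**What the plan says.** **Covariates.** Section 11.1 assigns a linear mixed model to postoperative NRS pain. It then lists age, BMI, ethnicity, education, marital status, vaginal parity, ASA class, medication, intoxications, chronic pain, surgical history, indication and type of surgery. The list is introduced as examples, and the variables "will be considered in the statistical analysis. These are taken into account because these variables can be possible confounders". Section 9.1.3 repeats that they can be confounders. No section says which variables enter, by what criterion, in what coding, or whether the adjusted or the unadjusted result is primary. Section 9.2 makes the trial open label.

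**How some listed items are recorded.** Question 13 of Attachment 2 asks "Do you have chronic pain (existing for more than 6 months) not related to the reason of the surgery". Section 5.3 excludes "persistent or recurrent pain lasting longer than 3 months", with the qualifier "The pain is not due to the gynecological problem". Indication is a blank line, "Indication of surgery (will be filled in by your doctor", and medication use is also free text. Type of planned surgery has no field in Attachment 2, although sections 9.1.3 and 9.3 say it is collected.

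**STAI-6 and PCS.** Section 3 lists "Pre-operative anxiety (State-Trait Anxiety Inventory (STAI)-6 questionnaire" as a secondary outcome, and section 9.1.2 lists "Pain catastrophizing (Pain Catastrophizing Scale questionnaire" likewise. Section 9.3 times both at T0: "After receiving written informed consent and before randomisation, pre-operatively a baseline questionnaire pre-operative anxiety (STAI-6 questionnaire", followed by the PCS. From T1 to T3 only NRS pain and NRS anxiety are scored. Section 9.3 calls the STAI a baseline measure, and section 11.2 plans t-tests on both questionnaires to check that the groups are balanced.

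**The concern.** With no fixed set, two analysts who both follow section 11.1 can fit different primary models, and the choice can be made after open-label outcomes have been seen. At stake are the reproducibility of the primary estimate and its power. Three measures that precede any VR, and are plausible candidates for adjustment, are not on the list.

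The second issue is one of labelling. VR cannot affect a questionnaire completed before allocation. Reporting STAI-6 and PCS as outcomes would present chance differences as results.

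**Working it through.** **1. The plan's own sample size.** Section 5.4 gives a difference of 15 mm, SD 20 mm, alpha 0.05, power 0.8, 26 per group and 30 with loss to follow-up. Assuming a two-sided test, n = 2 × [20 × (1.960 + 0.842)/15]² = 27.9, so 28 per group by the normal approximation and 29 by the t-test. The stated 26 is 2 below the first figure. Its t-test power is 75.6%, and 30 per group gives 81.5%. These are the unadjusted reference values below.

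**2. Power for a between-group contrast on one postoperative score.** With k covariates and joint correlation R with pain:

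- d = 15/20 = 0.75; df = 2n − 2 − k
- noncentrality = d × √(n/2) × √(1 − q) / √(1 − R²)
- q is the chance imbalance, averaged over Beta(k/2, (2n − 1 − k)/2), with mean k/(2n − 1).

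For n = 26 and k = 0 the noncentrality is 0.75 × √13 = 2.704 on 50 df, giving 75.6%. With 13 covariates the mean of q is 13/51 = 0.25; with two it is 2/51 = 0.04.

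| Model | 26 per group | 30 per group |
|---|---|---|
| Unadjusted | 75.6% | 81.5% |
| Two covariates, R = 0 | 73.8% | 80.1% |
| Two covariates, R = 0.5 | 85.0% | 89.9% |
| 12 unrelated, one parameter each | 63.3% | 71.6% |
| 13 unrelated, one parameter each | 62.1% | 70.6% |

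At 26 per group, two covariates give 75.5%, 77.7% and 80.8% at R = 0.2, 0.3 and 0.4. They break even at R of about 0.2.

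**3. The same question in a mixed model.** This was simulated with a random intercept, T2 and T3 as outcomes, an effect of 0 at T2 and 15 at T3, within-patient correlation 0.3 to 0.7, complete data and 26 per group. Power for the T3 contrast was 76–78% unadjusted, 74–75% with two covariates at R = 0, 86–87% at R = 0.5, and 64–67% with 13 unrelated covariates.

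**4. Group-by-time contrast.** In 20 fitted models with complete data, adding two baseline covariates as main effects changed the group-by-time estimate by less than 10⁻¹⁴.

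**5. Type I error (nominal 5%).** Same model, within-patient correlation 0.5, 12 candidate covariates:

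- a fixed pair: 4.6–5.3%
- screening on association with outcome: 4.0–4.9%
- a 10% change-in-estimate rule: 4.9–6.3%
- reporting the most favourable of no covariate or any single one: 7.9–10.0% (10.8% with 13 candidates).

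**6. STAI-6 and PCS as outcomes.** Any difference after proper randomisation is chance. Two independent tests at 0.05 give 1 − 0.95² = 9.75% probability of at least one nominally significant result.

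**7. Chronic pain item.** A woman answering yes to question 13 has had pain for more than 6 months unrelated to the surgery. She therefore also meets the more-than-3-months exclusion, so the answer should be no for every eligible patient.

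**8. STAI-6 range.** Section 9.3 describes a 4-point scale anchored 0 to 4, but its reversal rule uses 1 to 4 and Attachment 3 shows four options. Its formula gives 6 × 20/6 = 20 to 24 × 20/6 = 80. A score of 90 would need an item sum of 90 × 6/20 = 27, above the maximum of 24.

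**The case against.** The strongest reply is that the harm depends on a contrast the plan does not fix. Section 3 speaks of a reduction in postoperative pain score. That can be read as change from T2 to T3, and main-effect baseline covariates then do not matter. This stands, and it is why the power figures are conditional.

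It is also fair that section 11.1 says the variables are considered, not all entered. The 62.1% figure therefore shows one extreme and does not describe the plan. Nor is one parameter per variable the form's coding, since ethnicity, education and ASA class have several categories. All the candidates are pre-operative, so a set fixed without regard to the treatment result introduces no bias. The documents give no correlation of PCS or STAI-6 with postoperative pain, so that pair is an example only.

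A reader might infer from Attachment 2 that the list cannot be entered at all. The documents do not support that. Section 5.3 excludes only chronic pain not due to the gynecological problem, so chronic pain as named in section 11.1 may still vary; only question 13 is constant. Type of surgery could come from the patient file, which section 13.1 allows. Free text can be coded.

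What remains is that nothing in the plan fixes the covariates, and that the outcome lists contradict the schedule.

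**Conclusion.** The point holds as a should-fix.

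- **Covariates.** For a between-group contrast, the choice left open can change the estimate. At 26 per group it can move power from 62.1% (13 unrelated covariates) to 85.0% (two at R = 0.5), against 75.6% unadjusted. This assumes a two-sided test, d = 0.75 and correlations that are not in the documents. For a group-by-time contrast with complete data, main-effect covariates have no influence.
- **False positives.** A reader might infer serious inflation. Ordinary selection rules keep the rate near 5–6%. It reaches about 8–11% only if the most favourable of the unadjusted and single-covariate models is reported. A deliberate search over subsets could go higher, but section 11.1 proposes neither practice.
- **STAI-6 and PCS.** They are mislabelled as outcomes. The harm is small, because sections 9.3 (STAI) and 11.2 (both) already treat them as baseline.
- **STAI-6 scoring.** The anchors and the upper limit are a minor slip. They affect reported STAI values, not the adjusted treatment test if coding is consistent.

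**What to change.** **Section 11.1.** Name one primary model with a short covariate set, fixed and coded before outcome data are analysed. PCS total and STAI-6 at T0 are one example; another short set is acceptable with reasons. T1a pain may go in the primary model or in one sensitivity analysis, with a note that it precedes VR but follows open-label allocation. T1b must not serve as baseline, because it follows VR in the VR group. Keep the 13 variables for baseline description or one labelled sensitivity analysis.

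**Recording.** State where type of surgery is recorded. Reconcile question 13 of Attachment 2 with section 5.3. Leave chronic pain out of the model only if question 13 is its sole source.

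**Sections 3, 9.1.2 and 11.2.** Relabel STAI-6 and PCS as baseline measures and drop their between-group significance tests.

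**Section 9.3.** Score STAI-6 items 1 to 4, range 20 to 80.

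**Cost.** Wording in sections 3, 9 and 11 and Attachment 2, with notification to the METC under section 13.3 if a favourable opinion has already been given. The three candidate covariates are already collected. If two fixed covariates prove unrelated to pain, power falls by 75.6 − 73.8 = 1.8 points at 26 per group, or 81.5 − 80.1 = 1.4 points at 30.
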